## 5.6 Adverse Reaction and Their Management

Reporting adverse or unanticipated events: Investigators do not anticipate needing to remove a subject from the study for any adverse events. Subjects may decline to participate or withdraw their consent, as per standard policies and procedures. If a circumstance arose where the investigators were concerned about a subject's safety as a result of the study, the subject would be removed from the study. The proposed research will comply with the regulations set forth in CFR Part 46, Protection of Human Subjects. All staff involved in the proposed protocol have been educated regarding HIPAA regulations and fully understand their responsibility to safeguard the personal health information of every participant involved in the research.

Anticipated reactions: Adverse reactions are expected to be minimal. A possible adverse reaction as a result of participating in this study is psychological distress as a result of viewing the informed consent (IC) video and booklet, which discuss the fact that chemotherapy does not cure metastatic colorectal cancer. The IC booklet also includes an optional section that discusses typical life expectancy with and without chemotherapy. This optional section is sealed, and is preceded by a cautionary sign with explanation that normalizes patients' decision of whether or not to review it. The video similarly includes an optional web-link to a segment discussing life expectancy. This optional video web-link is also preceded by a cautionary explanation that normalizes patients' decision of whether or not to view this segment. Participants may also find some survey items regarding their prognostic understanding to be distressing; however we have worded these items carefully and with the input of patient stakeholders to ensure their sensitivity and acceptability to patients.

Reaction management: As explained above, our intervention is designed to minimize patient distress by making information about life expectancy completely optional and easy to avoid. Furthermore, patients will not be eligible for this study until after they have received an initial chemotherapy recommendation from their oncologist, a conversation which would have covered the fact that chemotherapy is not intended to cure metastatic colorectal cancer and may also have included conversation about prognosis. As mentioned above, sensitive aspects of the survey were carefully worded with the input of patient stakeholders to minimize potential for distress. Participants will be reminded that they may skip portions of the questionnaires that they find discomforting.

For any patient who exhibits severe distress as result of the study procedures, the study research assistant will notify the patients' oncologist and social worker for appropriate response, including possible mental health referral if necessary. Furthermore, participants will be reminded that participation is voluntary and can be stopped at any time for any reason.

The qualitative interviews, specifically, will include questions about prognosis. These questions are sensitive and may precipitate an emotional reaction for some patients. We propose the following plan should the patient exhibit mild, moderate, or severe distress during the interview.

- Mild distress: The research assistant will pause the interview, and ask the patient if they would prefer to skip the interview question or end the survey all together. The patient will be reminded that answering the qualitative question is entirely voluntary, and study participation is voluntary and can be ended at any time. At the end of the interview, or should the

**Title:** Improving Informed Consent for Palliative Chemotherapy: RCT of Usual IC versus Investigational IC

**Overall PI:** [name], Dana-Farber Cancer Institute

**Dana-Farber protocol version no./date:** v17 / August 30, 2017

participant choose to end the interview, the research assistant will offer to contact a member of that patient's care team (nurse, social worker, primary nurse practitioner, or physician) to inform them of the event, or to speak with the patient in person (if the interview is taking place in clinic) or by phone.

- Moderate or severe distress: the research assistant will stop the interview, and immediately notify the patients' treating physician or nurse practitioner by page for immediate attention. They will also page the social worker on call for the DFCI GCC.

For any caregiver who exhibits severe distress as result of the study procedures, the study research assistant will notify the study PI, [name]. [name] will personally facilitate obtaining the appropriate support for the caregiver in distress, including possible mental health referral for the caregiver if necessary. Furthermore, caregivers will be reminded that participation is voluntary and can be stopped at any time for any reason.

All sites should notify the Overall PI, [name], MPH, at [[name]](mailto:[contact]) or [contact] within 24 hours of an adverse reaction. [name] will notify the patient's primary oncologist and the Dana-Farber IRB, as appropriate. In concert with the primary oncologist, [name] will ensure the patient received appropriate follow-up care.

## 5.7 Privacy and Confidentiality

### **Privacy Protections:**

Participants will be recruited and consented in-person in the clinic or via phone. The research assistant obtaining informed consent will ensure that these conversations occur in private or semi-private settings where others cannot overhear. If the participant signs consent, they will be given standard institutional Informed Consent materials which they can review silently (as these are paper documents) or the investigational IC materials (booklet and video) which they can review in private (if a private room is available) or in semi-private (in this case, we will ask the participant to watch the video using earphones to protect the patient's privacy).

Participants will be asked to complete 3 questionnaire-based assessments during the study period. If these are done in-clinic and if a private room is available, the research assistant may read the questions aloud to the participant and record the participant's answers, or the participant may complete the questionnaire silently using a study-provided iPad. If these are done via phone, the research assistant may read the questions aloud to the participant and record the participant's answers; the research assistant will conduct the phone questionnaire from a private location. In some instances, the central research assistant at Dana-Farber may email the REDCap questionnaire link to a participant; the participant will open the link, enter the survey using their unique study ID number, complete and submit the questionnaire online. The questionnaire will not request PHI and will be administered online using REDCap, a HIPAA-compliant, Partners'-managed electronic data capture platform.

Participant questionnaire responses will be recorded in a de-identified fashion using unique study ID numbers. The only key linking these unique study ID numbers to the participant's identity will be maintained by the study research assistant in a password-protected spreadsheet saved in a secure network folder. Hard-copy signed informed consent documents will be kept in the research assistant's locked drawer. At Dana-Farber, this is located at their Dana-Farber desk (Dana Bldg, 10th floor). Any hard-copy study documents will be kept in a study file in the research assistant's locked drawer

**Title:** Improving Informed Consent for Palliative Chemotherapy: RCT of Usual IC versus Investigational IC

**Overall PI:** [name], Dana-Farber Cancer Institute

**Dana-Farber protocol version no./date:** v17 / August 30, 2017

separately from the signed informed consent documents.

Once the study is complete, the data collected will be aggregated and analyzed. All dissemination of results be aggregated and de-identified.

**Confidentiality Protections:**

The following information will be collected from or about study participants using unique study ID numbers (the only key linking these unique study ID numbers to the participant's identity will be maintained by the study research assistant in a password-protected spreadsheet saved in a secure network folder).

Medical record Abstraction: Baseline abstraction will collect date of diagnosis and stage at diagnosis, prior cancer surgeries, prior adjuvant or palliative chemotherapy and dates of administration, date of metastatic recurrence (if relevant), comorbid medical conditions, performance status. Post-decision abstraction will collect treatment decision made (e.g. what chemotherapy regimen, clinical trial, no chemotherapy). Follow-up abstraction will collect changes

**Title:** Improving Informed Consent for Palliative Chemotherapy: RCT of Usual IC versus Investigational IC

**Overall PI:** [name], Dana-Farber Cancer Institute

**Dana-Farber protocol version no./date:** v17 / August 30, 2017

in treatment (e.g. dose reductions, change in chemotherapy), ER visits or hospitalizations, results of restaging scans (disease progression, stable disease, or response), and medical record documentation of advance care planning.

Questionnaire Administration: The baseline assessment will assess socio-demographics, information/communication preferences, decision control preferences, and illness understanding. Post-decision survey will assess core understanding required for informed consent (IC) (risks, benefits, alternatives), understanding of illness (diagnosis, curability), decisional conflict, satisfaction with the IC materials, satisfaction with communication, and anxiety. Follow-up survey will assess changes in treatment and illness understanding, decisional regret, communication satisfaction, care satisfaction & anxiety.

The raw data will only be shared with the study team at Dana-Farber Cancer Institute. Once the study is complete, the data collected will be aggregated and analyzed. All dissemination of results be aggregated and completely de-identified.

Data collected from this study will be retained for 5 years post study completion.

Hard-copy study materials will be kept in the research assistant's locked drawer. At Dana-Farber, this is located at their Dana-Farber desk (Dana Bldg, 10th floor). Electronic data will be kept in password-protected spreadsheets saved in a secure network folder accessible only to study team members and maintained by Dana-Farber IS. Data will be captured using REDCap, a HIPAA-compliant, Partners'-managed electronic data capture platform.

**Title:** Improving Informed Consent for Palliative Chemotherapy: RCT of Usual IC versus Investigational IC

**Overall PI:** [name], Dana-Farber Cancer Institute

**Dana-Farber protocol version no./date:** v17 / August 30, 2017

## 6.0 STATISTICAL ANALYSIS

We will test hypotheses that the study intervention---informed consent (IC) video/written tools developed with patient and clinician input---can improve patient-centered decision making for subjects contemplating palliative chemotherapy for advanced GI cancer.

**Objective 1:** Determine if the multi-media informed consent (IC) tools improve patients' understanding of benefits and risks of palliative chemotherapy as compared to the standard IC process.

*Hypothesis:* The multi-media IC tools will decrease the likelihood that patients overestimate the curative potential of palliative chemotherapy as compared to the usual IC process. (primary study outcome)

*Hypothesis:* The multi-media IC tools will increase the likelihood that patients understand the goal of treatment as compared to the usual IC process.

*Hypothesis:* The multi-media IC tools will increase the likelihood that patients will have an accurate understanding of the risks of chemotherapy as compared to the usual IC process.

**Objective 2:** Determine if the multi-media informed consent (IC) tools decrease decisional conflict, increase the likelihood patients achieve their preferred role in decision-making, and increase satisfaction with the chemotherapy IC process as compared with the standard IC process.

*Hypothesis:* The multi-media IC tools will decrease decisional conflict as compared to the usual IC process

*Hypothesis:* The multi-media IC tools will increase the likelihood that patients achieve their preferred role in treatment decision-making as compared to the usual IC process

*Hypothesis:* The multi-media IC tools will increase satisfaction with the chemotherapy IC process as compared to the usual IC process

**Objective 3:** Determine if the multi-media informed consent (IC) tools enhance patients' prognostic understanding, increase advance care planning, and facilitate patient-physician conversations about end-of-life care preferences.

*Hypothesis:* Patients randomized to the intervention will have more realistic expectations of their prognosis as compared to patients randomized to the usual IC process.

*Hypothesis:* Patients randomized to intervention will be more likely to have designated a healthcare proxy and more likely to have a DNR order as compared to patients randomized to the usual IC process

*Hypothesis:* Patients randomized to the intervention will be more likely to discuss their end-of-life care preferences with their healthcare proxy, and with their oncologist as compared to patients randomized to the usual IC process.

We will adhere to standard reporting principles delineated by the CONSORT statement for conduct and reporting of randomized trials. Primary reports will reflect the as randomized, "intention to treat" principle, however, we will also describe results according to actual exposure to the study interventions (based on patients' self-report of whether they reviewed the standard-of-care, or investigational chemotherapy informed consent materials). Fisher's exact test will test the difference between the study arms in the first primary outcome (the proportion of patients at follow-up assessment who fail to understand that chemotherapy is "not at all likely" to cure their cancer, as assessed by an item from CANCORS). We will also test the influence of the intervention on secondary outcomes (e.g. understanding of the goal of palliative chemotherapy, chemotherapy risks, decisional conflict,

**Title:** Improving Informed Consent for Palliative Chemotherapy: RCT of Usual IC versus Investigational IC

**Overall PI:** [name], Dana-Farber Cancer Institute

**Dana-Farber protocol version no./date:** v17 / August 30, 2017

achievement of preferred role in decision-making, satisfaction with chemotherapy IC process, prognostic understanding, advance care planning, discussion of end-of-life care preferences, satisfaction with MD communication, satisfaction with informed consent (IC) documents, decisional regret, emotional distress) using Fisher's exact or chi-square tests for dichotomous outcomes, and t-tests or Wilcoxon tests for linear outcomes. For missing data for primary or secondary outcomes, we will employ multiple imputation under a missing at random assumption.

Subset analyses will explore the effect of the intervention on 1) patients making a decision about 1st line treatment, 2) patients making a decision about 2nd line treatment, 3) patients with colorectal cancer, and 4) patients with pancreatic cancer.

Because the effects of our intervention may be moderated by patient characteristics (e.g. age, race/ethnicity, health literacy and numeracy, communication preferences, decisional control preferences), we plan to conduct exploratory analyses investigating whether these factors moderate the effect of the intervention on outcomes including 1) accurate understanding of chemotherapy benefits, 2) satisfaction with communication and the IC tools, 3) decisional involvement, or 4) emotional distress. For example: we hypothesize that the IC tool may lead to decreased distress among patients who prefer a detail-oriented prognostic communication style, whereas it may lead to increased distress among patients who prefer a vague and support-focused prognostic communication style. We would also hypothesize that the effects of

**Title:** Improving Informed Consent for Palliative Chemotherapy: RCT of Usual IC versus Investigational IC

**Overall PI:** [name], Dana-Farber Cancer Institute

**Dana-Farber protocol version no./date:** v17 / August 30, 2017

the intervention may be greater among patients with higher health literacy scores. We will test these hypotheses using multivariable logistic or linear regression analyses (depending upon the dependent variable), including interaction terms for collinear factors, and controlling for potential confounding factors (e.g. age, race/ethnicity, marital status).

**Power:** In the CANCORS study, 80% of mCRC patients on 1st line chemotherapy thought that chemotherapy could potentially cure their disease (median of 4 months post-diagnosis). Based on previous series and projections about our patient mix, we anticipate that 60% of patients will have inaccurate expectations about the benefits of chemotherapy. If the intervention strategy is able to better align expectations with likely outcomes by one third (33%) we will deem the intervention as having major impact. If this benchmark 33% reduction is not achieved but the intervention exposed subjects nonetheless have expectations that are more accurate, we will view the intervention as beneficial but lacking major impact. Assuming a baseline 60% rate of inaccurate expectations about the benefits of chemotherapy, with a total of 194 patients, we will have 80% power to detect a 33% decrease (20% absolute decrease) in inaccurate expectations among patients exposed to the intervention with a one-sided type I error of 2.5%.

Open-ended comments in the patient and caregiver follow-up surveys regarding prognostic understanding will be transcribed verbatim with removal of all potential identifying information (e.g. names). The transcribed responses will then be analyzed using standard qualitative techniques. Borrowing from principles of grounded theory, comments will be reviewed by two or more members of our research team until a set of themes emerges. Themes will be compared and revised in an iterative process with input from the lead study investigators as necessary to resolve differences. A coding manual will be developed using the final coding schema. Using this coding framework, each participant's response will be analyzed line-by line by two independent coders. Coders will be blinded to the participants' randomization group, although if the participant mentions the intervention within their response, this will not be stricken from the transcripts.

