**Procedure for randomization (see schema on page 2):**

1. For patients making a chemotherapy treatment decision at the time of study enrollment: After study consent and the baseline assessment, the study team will then randomize the patient to either the Usual IC Arm or the Investigational IC Arm of the study using REDCap's 1:1 randomization algorithm, stratified by 1st-line or 2nd-line chemotherapy.
2. For patients NOT making a new chemotherapy treatment decision at the time of study enrollment (e.g., they are receiving ongoing treatment with first-line palliative chemotherapy), randomization will occur at the point at which the patient is faced with a new chemotherapy treatment decision (e.g., for cancer progression, or treatment-related toxicity). Research assistants will contact the treating oncologists prior to scheduled chemotherapy visits and/or restaging visits to remind them of their patient's participation on the study, and to request that the oncologist contact the research assistant in the event that a new treatment decision is being made. When the patient's oncologist confirms that the patient is faced with a new chemotherapy treatment decision, the study team will then randomize the patient to either the Usual IC Arm or the Investigational IC Arm of the study using REDCap's 1:1 randomization algorithm, stratified by 1st-line or 2nd-line chemotherapy. Patients who do not make a new treatment decision during the timeframe of this study will not be randomized, and will not complete future study assessments.

Participants will be randomized 1:1 without blinding to receive either Usual Informed Consent or Investigational Informed Consent by utilizing a randomization algorithm managed by REDCap. This will be stratified according to whether the patient is 1st line palliative chemotherapy or 2nd line palliative chemotherapy.

The name and telephone number of the research study person who will be responsible for registration and randomization is: [name], [[name]\\[contact]](mailto:[contact]), [contact].

When registering subjects, the study team will ask for the following information (see Appendix B):

- Name, telephone number, and email address of research assistant enrolling the participant
- Date subject signed informed consent

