The follow-up assessment will be administered by the central study research assistant at Dana-Farber at any point between 2 months post-chemo start and 3 months post-chemo start. During this 1 month period, the study research assistant will follow-up with the participant and caregiver up to 3 times each. One follow-up is defined as: an in-person approach OR a phone call with an accompanying email. If the participant is non- responsive after 3 attempts, then the study research assistant will mark the follow-up assessment as missing and will not contact the participant about the follow-up assessment again.

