## 5.0 STUDY DESIGN AND METHODS

### 5.1 Design/Study Type

Non-treatment intervention, randomized clinical trial of up to 350 participants [244 patient participants plus up to 106 of their caregivers as caregiver participants] (social behavioral research).

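### The 80% power stated at 194 patients is not the power of the named primary test (Fisher's exact, 76.4%), and no rule turns the imputed data sets into one primary result

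*Combined protocol and SAP*

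**What the plan says.** Section 6.0 (Statistical Analysis) assigns Fisher's test to the primary outcome, the proportion at follow-up who do not answer that cure is not at all likely: "exact test will test the difference between the study arms in the first primary outcome". For secondary outcomes the section is looser and permits Fisher's "exact or chi-square tests for dichotomous outcomes".

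The Power paragraph of Section 6.0 starts from "Assuming a baseline 60% rate of inaccurate expectations about the benefits of chemotherapy" and states that "with a total of 194 patients, we will have 80% power to detect a 33% decrease (20% absolute decrease"), at a one-sided type I error of 2.5%. It does not name the test behind that figure.

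Section 5.1 gives the trial size as "244 patient participants plus up to 106 of their caregivers as caregiver participants". Section 4.0 has two provisions that separate enrolled from analysed patients. On randomization: "Patients who do not make a new treatment decision during the timeframe of this study will not be randomized". On assessments, if there is no response after three attempts, "then the study research assistant will mark the follow-up assessment as missing". Section 5.4 makes that follow-up assessment the primary time-point.

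For missing primary or secondary outcomes, Section 6.0 says "we will employ multiple imputation under a missing at random assumption", with a literature reference. It gives neither the number of imputations nor a way of combining results across them.

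**The concern.** A power figure describes a particular test. Fisher's test is conservative for a two-arm binary comparison of this size, so a sample size from the ordinary chi-square formula does not give it the same power. If 194 is the number analysed, the chance of missing the planned effect is 23.6% (100 − 76.4), not 20%.

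The second gap concerns the result itself. Rubin's rules combine estimates and their standard errors. Fisher's test supplies a p-value, and the plan names no effect estimate for the primary outcome. The analyst must therefore choose how to get from the imputed data sets to one primary p-value. In a trial randomized without blinding (Section 4.0), that choice should be on record before results by arm are visible, particularly since some natural choices do not hold the error rate at 2.5%.

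**Working it through.** **Inputs from the documents.** Control rate 0.60, intervention rate 0.40, one-sided alpha 0.025, total 194 and power 80% (Section 6.0, Power); 1:1 allocation, so 97 per arm (Section 4.0); Fisher's test (Section 6.0); 244 patients (Section 5.1).

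**Reproducing the plan's figure.** Uncorrected two-proportion formula with pooled variance under the null:

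n per arm = [z(0.975)·√(2·0.5·0.5) + z(0.80)·√(0.6·0.4 + 0.4·0.6)]² / 0.20²
= [1.960·0.7071 + 0.8416·0.6928]² / 0.04 = 96.9, so 97 per arm and 194 in total.

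The same approximation gives 80.03% power at 97 per arm. The stated 194 and 80% are thus those of an uncorrected chi-square-type calculation. The continuity-corrected formula, which is closer to Fisher, gives 106.7, so 107 per arm (214 in total).

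**Exact power at 97 per arm.** Sum Bin(x; 97, 0.6)·Bin(y; 97, 0.4) over all tables that the test rejects at one-sided 2.5%:

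| Test | Power | Size, common rate 30% to 80% |
|---|---|---|
| Fisher | 76.4% | 1.6% to 1.9% |
| Uncorrected chi-square | 80.7% | 2.4% to 2.6% |

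Two-sided Fisher at 5% also gives 76.4%. With 58 of 97 inaccurate under usual consent, Fisher rejects at 43 or fewer in the other arm and chi-square at 44 or fewer.

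**From 244 downwards.** The loss rates are assumptions; the documents give none.

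| Analysed (loss from 244) | Fisher | Chi-square |
|---|---|---|
| 244 (0%) | 84.9% | 87.7% |
| 220 (10%) | 81.5% | 84.9% |
| 208 (15%) | 77.6% | 81.5% |
| 196 (20%) | 77.2% | 81.3% |
| 194 (20.5%) | 76.4% | 80.7% |

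Fisher's power is saw-toothed: 80.1% at 204, 77.5% at 206. It stays at 80% or more only from 216 analysed, a loss of at most (244 − 216)/244 = 11.5%.

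**Sensitivity to the control rate.** At 194 analysed, with the same one-third cut:

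| Control rate | Fisher | Chi-square |
|---|---|---|
| 55% | 68.6% | 73.6% |
| 60% | 76.4% | 80.7% |
| 65% | 83.2% | 86.6% |

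**Combination rule.** These figures are simulated on inputs that are not in the documents: 244 randomized, 35% second line, 21% of follow-up missing depending on line and post-decision answer, odds ratio 2 or 7.4 between post-decision and follow-up answers, 20 imputations within arm, line and post-decision answer.

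| Rule | Power at 60% v 40% | One-sided size |
|---|---|---|
| Median of the Fisher p-values | 83% | 3.0% to 3.2% |
| Mean of the Fisher p-values | 77% to 78% | 2.0% |
| Risk difference pooled by Rubin's rules | 80% to 81% | 2.6% to 2.7% |
| Fisher on observed cases, no imputation | 75% to 76% | 1.7% to 1.9% |

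**Size if the primary test were changed.** Exact enumeration over every even total from 194 to 244, no missing data, common rates 30% to 80%: chi-square size reaches 2.9% (totals 204 and 234) and the unpooled risk-difference test 3.0% (totals 206 and 238), all at a common rate of 50%.

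**The case against.** The power gap is small. It is 3.6 points (80 − 76.4) and one patient at the decision boundary in the example. The planning assumption matters far more: a control rate of 63% with the same one-third cut would give Fisher 80.6% at 194, and moving from 55% to 65% shifts power by 14.6 points (83.2 − 68.6). The 60% itself is a projection, set against 80% in the survey that the plan cites. All of this stands, and it limits the weight of the first half of the point.

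The planned 244 would give Fisher 84.9%. That is correct arithmetic, but it requires every enrolled patient to be randomized and to have the primary outcome, and Section 4.0 provides for exceptions to both.

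The imputation figures depend on invented inputs. That also stands: they show that the rule matters, not what this trial will experience. The absence of a rule does not depend on them.

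One might answer that the plan should simply switch to chi-square, which matches the stated 80%. But Fisher is valid, and the substitutes do not hold 2.5% at every sample size. The protocol is at v17, and Section 5.5 suggests surveys are already being administered, so replacing a named exact test with a less conservative one would need its own justification.

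A reader might infer that the trial is underpowered, or that its primary test is biased. The documents support neither. They do not say that 194 is the number to be analysed, and Fisher on complete data keeps its error rate below 2.5%. A reader might also infer that the combination rule was left open in order to be chosen later. Nothing in the documents suggests that.

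**Conclusion.** The point holds as a mismatch and a gap in specification. The stated 80% at 194 is not the power of the named test, which is 76.4% if 194 patients are analysed 1:1 and the rates are 60% and 40%. This part is exact and needs no outside assumption. Whether the trial falls short of 80% cannot be settled from the documents, because 194 and 244 are not connected and no loss rate is given; the dividing line is 216 analysed. The shortfall is minor beside the uncertainty in the control rate.

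The missing combination rule is the stronger half. As written, the primary p-value is not determined by the plan whenever a follow-up answer is missing. Under the assumed 21% missing, the combination rules tried give power of about 77% to 83% and size of about 2.0% to 3.2%. Those ranges are conditional on the simulation inputs. The change is worth making, but the design itself is not put in doubt.

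**What to change.** In Section 6.0:

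1. Keep Fisher as the named test. Name the test behind the power figure and restate power as about 76% at 194 analysed and 84.9% at 244 analysed. Say whether 194 means randomized or analysed, and how it relates to 244 through assumed non-randomization and loss.
2. Before outcome data by arm are seen, state how the imputed data sets give one primary result and how many imputations are used. For example, compute the difference in proportions with an inaccurate answer and its standard error in each imputed data set, pool by Rubin's rules with a 95% CI, and report it with Fisher on observed cases. Say which of the two is primary. A pooled difference would also give an effect size to set against the plan's one-third benchmark.

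An option, not preferred, is to make an uncorrected chi-square or pooled risk difference the primary test. It would match the stated 80%, at the price of one-sided size up to 2.9% or 3.0% at some totals between 194 and 244. The same price applies if the pooled difference in step 2 is declared primary. Either change needs a record that it was made without sight of results by arm.

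The cost is a few sentences, with no new patients, visits or data. Keeping Fisher means accepting a lower stated power at 194.
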